- 9- Even if such collaboration is effective, it may not be scalable due to a limited number of geriatric healthcare providers.

As a result, an automated geriatric co-management program, if shown to be feasible and as effective as in-person geriatric co-management, could be used to provide peri-operative geriatric care routinely in institutions that have limited or no geriatrics services.

The Electronic Rapid Fitness Assessment (the eRFA) at Memorial Sloan Kettering Cancer Center (MSKCC)

The eRFA was developed at MSKCC through collaboration between the Geriatrics Service and the Web Survey Core Facility (Webcore) in 2015. During the eRFA development process, the Geriatrics Service held multiple discussions to determine which GA domains to assess and which validated assessment methods to use. The name “Electronic Rapid Fitness Assessment” was selected to reflect the purpose of the GA, which is to distinguish patients who are fit from those who are frail.

Administration and Reporting of the eRFA:

The eRFA was first implemented in the Geriatrics clinic. In 2016, the Thoracic surgery clinic implemented the eRFA at the point of care. All patients who present to MSKCC geriatric clinics or thoracic surgery clinics complete the eRFA while they are waiting to be seen by their healthcare providers for their initial consultation. Patients may complete the eRFA on their own or with assistance from others (e.g., a caregiver), or they may allow someone else

(e.g., a caregiver) to complete the assessment for them. Patients may also complete the eRFA at home, before their appointment, if they have Internet access and an e-mail account. After the assessment has been completed, a registered nurse (RN) performs a cognitive assessment using the Mini-Cog[17, 18] and establishes the patient's mobility using the Timed Up and Go (TUG)[19] test, the results of which are then entered into the eRFA by the RN. The Mini-Cog and TUG assessments will be omitted if the patient is being seen via telemedicine.

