7.1 ASSESSMENT/EVALUATION PLAN

Assessment and Measurement Instruments:

In this study, the data will be collected using the following instruments and measurements methods:

- Electronic Medical Record review:

- 1- For patients in the intervention group (automated geriatric co-management), we will assess the percentage of recommendations that were followed by the surgery team. For example, if automated geriatric co-management recommends consultation with physical therapy perioperatively, we will assess whether the consult has been obtained.
- 2- For patients in both groups, we will assess the adverse surgical events by day 30 following surgery. Adverse surgical event is a composite of surgical complications grade 2 or higher, mortality after surgery, or discharge to any place other than home, or prolonged length of stay (defined as length of stay longer than 75% of the cohort who underwent the same surgical procedure), or readmission to the hospital within 30 days from surgery.

MSKCC's secondary surgical events database in the EMR has been shown to accurately record major postoperative complications within the 30 days after surgery[34].

- 3- to assess sociodemographic characteristics (age, gender, ethnicity),
- 4- to assess routine preoperative blood work (complete blood cell counts, chemistry panel).
- 5- To assess cancer characteristics (stage, receipt and type of neoadjuvant treatment)

- 6-** To assess surgical characteristics (type of surgery: minimally invasive vs open, duration of surgery, intraoperative blood loss, and American Society of Anesthesiologist Physical Status classification)
- **Four Meter Walk Test:** In order to assess functional recovery, the 4-meter walk test will be performed. In the 4-meter walk test, the time that it takes patients to walk 4 meters in their usual pace will be recorded in seconds by the clinical research staff. (This portion will be skipped for patients being seen via telemedicine.)

Assessment and Evaluation Plan

Patients will be screened for study eligibility at the time of attending their surgery appointment at MSKCC for consideration of surgery. The inclusion and exclusion criteria will be reviewed by the clinical research staff firstly to confirm the patients' eligibility status. Once eligibility has been determined and informed consent has been obtained, patients will undergo baseline assessments and subsequently randomization will occur.

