There will be two study visits for patients in both groups; baseline or pre-op visit (1st) and the 2nd visit. Baseline visit occurs at the time of new visit by the surgery team, or in the case that two months has passed since baseline, at the pre-op visit. 2nd visit occurs at the time of follow up after hospital discharge by the surgeons. Both baseline and 2nd visit may be conducted via telemedicine if preferred.

Baseline Study Visit/Pre-op Visit: In this visit, following assessments will be performed.

- The 4-Meter Walktest.
- Sociodemographic characteristics.
- eRFA completion per routine care

2nd Study visit: In this visit, following assessment will be performed.

- The 4-Meter Walktest.
- eRFA completion per routine care

Study participant follow up:

Thirty days after surgery:

- Collection of adverse surgical events (grade 2 or more complications, length of stay, readmission, disposition plan), surgery and cancer characteristics, and preoperative blood work results.

	Screening & Baseline study visit	Pre-operative visit	2 nd study visit (within 2 weeks of surgery)	30 Day post-surgery follow up
--	----------------------------------	---------------------	---	-------------------------------

Informed consent	✓			
------------------	---	--	--	--

Eligibility determination	✓			
Randomization	✓ (if proceeding with surgery in 2 months)	✓ (if two months have passed by from baseline visit)		
eRFA completion, per SOC	✓	✓ (if two months have passed since baseline visit)	✓	
Automated geriatric co-management program		✓	✓	
In-person geriatric co-management program		✓	✓	
4 MWT	✓	✓ (if two months have passed by from baseline visit)	✓	
Sociodemographic data	✓			
Preoperative lab results				✓
Cancer characteristics				✓
Surgical characteristics				✓
Adverse events				✓

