intervention will be deemed feasible if recommendations are followed for 50 patients. Finally, we will present the distribution of number of recommendations made and followed in the automated geriatric comanagement arm.

Secondary Aims

Effect of the automated geriatric co-management program compared to the in-person geriatric co-management on adverse surgical events.

All between-group comparisons will be by modified intent-to-treat (complete case analysis), with patients analyzed according to randomization, irrespective of whether they were proceeded to automated geriatric co-management or in-person geriatric co-management. To compare, by intervention arm, the proportion of patients with a composite outcome ("adverse surgical event") of either surgical complications grade 2 or higher, or prolonged hospital length of stay, or discharge to another care facility rather than home, or 30-day readmission to the hospital. Prolonged hospital length of stay will be defined as hospital length of stay greater than 75% of the cohort who underwent the similar procedure. We will test the association between intervention arm and adverse surgical event using logistic regression with the randomization stratum as the covariate.

It is plausible that the relative value of in-person vs. automated geriatric *co-management* depends on baseline risk, for instance, it could be that average risk patients are adequately managed by the automated approach, but those at high risk require individualized care. To this end, we will use a logistic regression with adverse surgical event as the outcome, study arm as the predictor, randomization strata as the covariate, and adjust for continuous baseline risk using the MSK-FI, with restricted cubic splines with knots at the tertiles to allow for non-linearity. We will then visualize the risk in both intervention arms across baseline risk to provide an individualized estimate of benefit for a given level of baseline deficit. The MSK-FI is a frailty index defined by ten sets of comorbidities, and one component related to dependency on five activities of daily living. The former will be queried from the institutional database, and the latter is assessed using the bADL and iADL measures on the eRFA.[35]

Effect of the automated geriatric co-management program with in-person geriatric co-management on postoperative functional recovery.

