To compare, by intervention arm, postoperative functional recovery. We will consider postoperative functional recovery as reported by the patient, as well as assessed by the study team during the 2nd study visit. Patient-reported recovery will be measured by three domains reported on both pre and post-operatively: Karnofsky Performance Status, basic activities of daily living, and instrumental activities of daily living.

Clinician-evaluated functional recovery will be assessed through the Timed Up and Go

test and the 4MWT. This analysis will only be done for patients who have completed the assessment during in-person visit with the surgery team. Recovery of Karnofsky Performance status, defined as the same or better Karnofsky Performance status during the 2nd study visit compared to baseline, will be compared between groups using a logistic regression with randomization strata as covariates. Basic activities of daily living, instrumental activities of daily living, Timed up and Go test and 4MWT will be compared between groups by ANCOVA, with baseline score and randomization strata as a covariate.

In the case that patient's surgery occurs after two months of completing the eRFA, either the patient has to complete another eRFA within two months of surgery, which then will be the patient's new preoperative baseline eRFA, or in case of not completing the eRFA, the patient will be excluded from the study.

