Assuming a correlation of 0.5 between baseline and follow-up, and a standard deviation of 1.8 (as seen in our preliminary dataset for the basic activities of daily living, the score of which ranges from 0 to 14), with ~95 patients per arm (after an estimated 5% loss of patients due to drop out), the power for various effect sizes for our continuous secondary endpoints when analyzed using ANCOVA are shown in the table, where it can be seen that we have high power to detect small differences between groups. Sensitivity analyses will be conducted where missing outcome data will be imputed by Multiple Imputation using Chained Equations.

Difference between groups	Power
0.5	60%
0.67	84%
0.8	94%

In 2017, the surgical services had completed surgical procedures on more than 5000 patients aged 65 or older with a hospital length of stay of 2 days or longer. Therefore, we expect to enroll the 200 patients for our study in less than two-years. We expect most patients to be older (75+) but to ensure that younger patients are not overly represented, we will cease accrual of patients 65 – 74 after 60 are accrued (i.e. 30%).

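### Free improvement for the secondary TUG and 4MWT endpoints: as written, the ANCOVA drops patients whose postoperative test was measured but whose first visit was remote

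*Combined protocol and SAP*

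**What the plan says.** All references are to the combined protocol and SAP.

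- **Tests not done remotely.** Section 3.1, on administering the eRFA: "The Mini-Cog and TUG assessments will be omitted if the patient is being seen via telemedicine". Section 7.1, on the 4MWT: "This portion will be skipped for patients being seen via telemedicine".
- **Either visit may be remote.** Section 7.1: "Both baseline and 2nd visit may be conducted via telemedicine if preferred".
- **Analysis set.** Section 11.0 (Secondary Aims) makes every between-group comparison a modified intention-to-treat comparison on complete cases. For the clinician-evaluated tests it adds: "This analysis will only be done for patients who have completed the assessment during in-person visit with the surgery team". It does not say whether this means the baseline visit, the 2nd visit or both.
- **Model.** TUG and 4MWT, like bADL and iADL, "will be compared between groups by ANCOVA, with baseline score and randomization strata as a covariate".
- **Imputation.** Section 11.0 (Sample size): "Sensitivity analyses will be conducted where missing outcome data will be imputed by Multiple Imputation using Chained Equations". No variables for the imputation model are listed.
- **Repeat baseline.** The section 7.1 schedule repeats the eRFA and 4MWT at a pre-operative visit, but only if two months have passed since the baseline visit. Section 11.0 makes a repeat eRFA the new pre-operative baseline.

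No section says what happens when the baseline TUG or 4MWT is missing and the postoperative value is present.

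**The concern.** Take a patient whose first visit is by telemedicine and whose 2nd visit is in clinic. The postoperative tests exist and the baseline tests do not. A complete-case ANCOVA with the baseline score as covariate cannot use this patient. Imputing missing outcomes does not help, because the missing item is the covariate.

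The baseline covariate is there to gain precision. Here its absence would remove randomized patients whose endpoint was measured. The remaining set is those with both visits in person, which is smaller than the set with an outcome and may be less like the randomized population. The power table in section 11.0 is offered for the continuous secondary endpoints in general and allows for 5% dropout only, so it makes no room for this loss.

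**Working it through.** **Inputs from section 11.0:** about 95 per arm, SD 1.8 (from bADL), baseline to follow-up correlation 0.5, differences 0.5, 0.67 and 0.8. **Assumed:** two-sided 5%, since section 11.0 states alpha only for the primary aim; a remote share m at each visit; and a correlation r between the two visits' modes. The documents give neither m nor r.

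**Step 1, the plan's own table.** Residual SD = 1.8 × √(1 − 0.5²) = 1.559. A two-sample comparison at 95 per arm gives 59.9%, 84.2% and 94.3% by the normal approximation, and 59.5%, 83.8% and 94.0% by the t distribution. The plan states 60%, 84% and 94%, so the table reproduces. One-sided 5% would give 71%, 91% and 97% and does not fit. The rest uses the t distribution and the middle difference, 0.67/1.8 = 0.37 SD.

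**Step 2, who is analyzed.**
- Share with both visits in person: (1 − m)² + r·m(1 − m). These are the complete cases.
- Share with a postoperative test: 1 − m. These are the patients who could be kept.
- Of the latter, the share with a baseline: q = (first line)/(1 − m).
- Residual SD if all of them are kept with a filled baseline: 1.8 × √(1 − 0.25q).

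**Step 3, m = 30%.** The kept set is 95 × 0.7 = 66.5 per arm in every row.

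| r | Complete cases per arm | Residual SD, all kept | Power as planned | Power, all kept |
|---|---|---|---|---|
| 0 | 95 × 0.490 = 46.6 | 1.635 | 54% | 65% |
| 0.5 | 95 × 0.595 = 56.5 | 1.597 | 62% | 67% |
| 0.8 | 95 × 0.658 = 62.5 | 1.574 | 66% | 68% |
| 1 | 95 × 0.700 = 66.5 | 1.559 | 69% | 69% |

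First row in full: the standardized difference is 0.67/(1.559 × √(2/46.55)) = 2.07 as planned, and 0.67/(1.635 × √(2/66.5)) = 2.36 with all kept.

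**Step 4, other shares, as planned against all kept.**
- m = 10%: 75.5% against 78.5% at r = 0; 77.7% against 79.1% at r = 0.5.
- m = 20%: 65% against 72% at r = 0; 70% against 74% at r = 0.5.
- m = 40%: 42% against 57% at r = 0; 53% against 60% at r = 0.5.

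**Step 5, check by simulation.** With independent modes and 5,000 simulated trials per setting, complete case against mean-filled baseline plus indicator gave 75% against 77% (m = 10%), 65% against 72% (20%), 52% against 64% (30%) and 41% against 56% (40%). Type I error was about 5% for both methods and neither was biased, with remote mode assigned at random.

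**The case against.** The strongest reply is that the restricted set is declared: section 11.0 says openly that the clinician-evaluated tests are analyzed in in-person completers. That stands in part. If both visits must be in person, the exclusion is intended, though no reason is given for setting aside measured outcomes. If only the 2nd visit must be, the condition supports keeping these patients and the complete-case model works against it. The text does not settle which.

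Second, the size may be small. Sections 4.2 and 7.1 tie visit mode to patient preference, so the same patients may choose telemedicine twice. They then have no outcome either, and nothing is recovered. This stands, and it is why the range starts at zero.

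Third, the imputation sentence lists no variables, and chained equations can fill covariates. True, but the plan names only outcomes, and imputation is confined to a sensitivity analysis, so the main analysis would still drop these patients.

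Fourth, the delayed-surgery visit gives some patients a second chance at a baseline. It applies only after two months. It also cuts the other way: section 7.1 puts baseline assessment before randomization, but a patient randomized at the first visit whose surgery is then delayed could have a new baseline measured after randomization.

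Fifth, the eRFA records TUG in three bands (Figure 2 of section 3.1), and the SD of 1.8 comes from bADL. The calculation is therefore a rough guide, more so for TUG.

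A reader might infer that the plan biases the comparison between arms. The documents do not support this. Baseline assessment generally precedes randomization, and the simulation above shows no bias when mode is random. Remote 2nd visits are a separate missing-outcome question that keeping these patients does not answer.

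**Conclusion.** The point holds as a free improvement on two secondary endpoints. Followed as written, the plan drops randomized patients with a measured postoperative TUG or 4MWT when the first visit was remote, and the imputation as described does not restore them.

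Under the assumptions above, the power given up at 30% remote runs from about 11 points (independent modes) through 5 (correlation 0.5) to none (same patients remote twice). At 10% remote it is at most about 3. The true loss cannot be fixed from the documents. It is a loss of precision and representativeness.

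The primary feasibility aim is untouched, and the patient-reported KPS, bADL and iADL do not depend on an in-person visit. It would go too far to say that these endpoints are certain to be badly underpowered, since that needs a telemedicine share the plan does not give.

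**What to change.** In section 11.0:

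- State that the in-person condition for TUG and 4MWT applies to the 2nd visit.
- In the TUG and 4MWT ANCOVA, keep every patient with a postoperative value. Use a baseline measured before randomization where there is one. Otherwise set the baseline to the overall mean and add a missing-baseline indicator.
- In the chained-equations sensitivity analysis, include the baseline walk tests and the baseline and 2nd-visit KPS, bADL and iADL. Any further gain in power is likely to be small and depends on correlations the documents do not give.
- Report the numbers analyzed by arm and by visit mode at each visit.

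The cost is SAP wording and a little programming, with no new patients, visits or data. The change does not repair the three-category clinician-evaluated recovery endpoint in section 11.0, which needs an observed pre-operative value; its analysis set should be stated separately.

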5.3 Subject Exclusion Criteria

- 1) Unable to read or comprehend English
- 2) Not having a completed eRFA within the two months of undergoing surgery

Note) To avoid excluding patients based on item 2, patients have to complete another eRFA within two months of surgery.

- 3) Being discharged in one day or earlier from the hospital.

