10.1 CRITERIA FOR REMOVAL FROM STUDY

Patients will have completed their participation in this study after the 30-day post-surgery follow-up or the 2nd study visit, whichever occurs later, and will be considered off-study.

Participants will be removed from the study if:

- ✓ He/she chooses to withdraw consent for continued participation at any time
- ✓ The participant reports intolerable distress due to study participation
- ✓ He/she becomes ineligible for study participation as designated by the inclusion/exclusion criteria

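### A randomized patient whose surgery slips past two months without a repeat eRFA is excluded from the whole study, an unbudgeted post-randomization exclusion that may bias feasibility in either direction

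*Combined protocol and SAP*

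**What the plan says.** Three sections combine to produce the rule.

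- Section 5.3 lists as an exclusion criterion "Not having a completed eRFA within the two months of undergoing surgery". A note there, and the text of section 4.2, tell patients to repeat the eRFA to avoid this.
- Section 10.1 removes from the study any participant who "becomes ineligible for study participation as designated by the inclusion/exclusion criteria", with no limit to the period before randomization.
- Section 11.0, under functional recovery, says that if surgery comes after two months and the eRFA is not repeated, "in case of not completing the eRFA, the patient will be excluded from the study".

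The schedule table in section 7.1 randomizes at the baseline visit "if proceeding with surgery in 2 months" and at the pre-operative visit "if two months have passed by from baseline visit".

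For the secondary aims, section 11.0 describes a modified intent-to-treat, complete-case analysis, "with patients analyzed according to randomization, irrespective of whether they were proceeded to automated geriatric co-management or in-person geriatric co-management". For the primary aim it names two exclusions, no baseline impairment and crossover, and the sample-size text allows 5% and 20% for them. Section 7.1 takes both recommendation uptake and the 30-day adverse events from review of the electronic medical record.

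**The concern.** The condition for baseline randomization is a forecast. A patient can be randomized with a valid eRFA, have surgery postponed, miss the repeat, and then be removed from every analysis. The two events that decide this, the delay and the missed questionnaire, both come after randomization, and assigned care could influence either.

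Two things are at stake. For Aims 2 and 3, the arms compared may no longer be the arms randomized. For Aim 1, accrual continues until 77 evaluable patients are reached, so an excluded patient is in effect replaced. If uptake among excluded patients differs from uptake among the rest, the observed feasibility rate shifts.

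**Working it through.** **1. The plan's own design.** Inputs from section 11.0: null 55%, alternative 70%, one-sided alpha 5%, power 85%; stop if 21 or fewer of the first 38 succeed; feasible if 50 of 77 succeed. With X1 the successes among the first 38 and X2 those among the next 39:

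P(feasible | p) = sum over x = 22 to 38 of P(X1 = x) × P(X2 ≥ 50 − x).

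This gives 0.0477 at p = 0.55 and 0.852 at p = 0.70. A search for the Simon minimax design returns the same boundaries, so the stated design is correct. The question is who enters the 77.

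**2. Who can be affected.** Deferring randomization to the pre-operative visit removes patients already known to be beyond two months. What remains is patients randomized at baseline whose surgery then slips and who do not repeat the eRFA. The documents give no rate for this.

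**3. Whether the plan already covers it.**

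- The two named primary-aim exclusions do not include it.
- The allowance is 5% + 20% = 25%, all assigned to other causes. 77 / (1 − 0.25) = 102.7, or 103 per arm, in line with the stated figure close to 100. Adding an assumed 5% or 10% lapse gives 77 / 0.70 = 110 or 77 / 0.65 = 118.5, or 119.
- A complete-case analysis drops patients whose data are missing. The 30-day composite and recommendation uptake are not missing here, because they come from the medical record.
- Multiple imputation is planned for missing outcome data, but nothing says that excluded patients are kept for it.

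**4. Effect on the feasibility decision.** Let q be the fraction of otherwise evaluable patients excluded and a the proportion of them for whom at least half of the recommendations were followed. Both are assumptions. With a true rate of 55% in all such patients, the rate among those analysed is

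p = (0.55 − q × a) / (1 − q).

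For example, q = 0.05 and a = 0 gives 0.55 / 0.95 = 0.579. Putting p into the formula in step 1:

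| Adherence among excluded (a) | q = 5%: p | P(feasible) | q = 10%: p | P(feasible) |
|---|---|---|---|---|
| 0% | 0.579 | 12.3% | 0.611 | 27.7% |
| 27.5% (half the overall rate) | 0.564 | 7.9% | 0.581 | 12.9% |
| 55% (unrelated to lapse) | 0.550 | 4.8% | 0.550 | 4.8% |
| 80% | 0.537 | 2.9% | 0.522 | 1.6% |

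**5. Balance between arms.** Section 4.2 sends in-person patients to the geriatrics service before surgery. Section 3.1 says "All patients who present to MSKCC geriatric clinics or thoracic surgery clinics complete the eRFA", which gives that arm an extra occasion for a repeat. However, that sentence goes on to describe the initial consultation and names thoracic surgery clinics as well. Sections 4.2 and 7.1 also give both arms the same routine eRFA. The documents therefore support a possible imbalance but do not show one.

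**The case against.** The strongest reply is that the affected group is small and the bias has no known direction. Both an unexpected delay and a missed repeat are needed, and the rule is worded identically for both arms. Patients may complete the eRFA at home, the geriatrics visit may be by telemedicine, and nothing places that visit within two months of a postponed operation. All of this stands.

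A reader might infer that the automated arm loses more patients, or that the rule removes likely failures and so inflates feasibility. The documents support neither. The lapsed item is a patient questionnaire, whereas the endpoint is what the surgical team does, and no section links the two. The opposite direction is also plausible: some sample recommendations concern preoperative exercise and consultations, and a longer wait leaves more time for them.

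It can also be said that the plan openly claims only a modified intent-to-treat set. That softens the conflict with analysis by randomized arm but does not remove it, because the stated modification is complete-case and these outcomes are obtainable.

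Finally, a recent eRFA has uses beyond functional recovery. It generates the recommendations, defines who has an impairment, and supplies the activities-of-daily-living component of the MSK-FI. That is a fair reason to want a recent eRFA, but not to discard a randomized patient who lacks one.

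**Conclusion.** The point holds as a post-randomization exclusion that is written into the plan, absent from the primary-aim exclusion list and the 25% allowance, and not covered by the complete-case modification. It is limited to patients whose surgery slips unexpectedly after randomization. Unequal loss between arms is a risk, not an established fact.

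The sign of any feasibility bias is unknown. Under the assumed 5% to 10% exclusion, the chance of declaring feasibility at a true 55% ranges from 1.6% to 27.7%, against 4.8% when lapse is unrelated to adherence. The upper end needs 10% excluded with none of them adherent. Those rates are assumptions because the documents give none. The change should be made because it costs little; the figures do not show that the trial's result would be wrong.

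**What to change.** Apply the two-month eRFA criterion only up to randomization. In sections 5.3, 10.1 and 11.0 (and where the criterion is repeated in sections 1.0 and 4.2), state that:

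- a patient already randomized remains in the study;
- when no repeat is done, the most recent eRFA completed before randomization serves as baseline;
- 30-day outcomes and recommendation uptake are collected and analysed in the assigned arm.

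Report by arm the number of patients whose eRFA was more than two months old at surgery with no repeat. Add two sensitivity analyses: functional recovery omitting those patients, and feasibility counting such automated-arm patients as failures.

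The cost is protocol and SAP wording, with no new visits or patients. The downside is that a few patients carry an older eRFA, which adds some noise to the functional analyses, to the MSK-FI activities-of-daily-living component and to the impairment list behind the recommendations.
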